Aim 3 (A3). Evaluate the impact of the staff intervention on resident falls, accidents and injuries and on quality of life using a prospective experimental design that derives information from five sources: (1) resident interviews (2) staff informants (3) observational data (4) chart and (5) incident/accident report data.

Primary Hypothesis: The frequency of falls, accidents and injuries will decrease in the

intervention group, relative to the comparison group after implementation of the training intervention.

Secondary Hypotheses: 1. Resident quality-of-life as measured by affective state will improve in the intervention group, relative to the comparison group after implementation of the training intervention.

2. Resident behavior problems will decline in the intervention group, relative to the comparison group after implementation of the training intervention. Resident behaviors will mediate the relationship between the intervention and the falls/accidents/injuries outcome.

Trial design

This is a pragmatic, prospective, cluster randomized trial (facility level) design with three waves of data collection (baseline, 6- and 12-months) at 12 assisted living facilities in two New York regions. There will be three levels of clustering: facilities within regions, units within facilities and repeated measures on residents within units, with the regions fixed. On a rolling basis, six facilities will be selected at random and recruited in New York City and the nearby suburban counties (downstate region). Six facilities in the upstate New York region of Rochester will also be randomly selected. Three facilities in each region will be randomized to usual care or to the intervention on a 1:1 ratio. Facilities allocated to the usual care group will receive the intervention after completion of their 12 month data collection.

Methods: Participants, interventions and outcomes

Study setting

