This measure was based on the Shift Coupon, a form originally designed by nursing staff to provide a “quick, easy, anonymous, and non-threatening method to report adverse events,”²¹ and is in the form of a small note pad. BRDSs are intended to measure recognition and capture real time R-REM events. Hypothesis 2, regarding enhanced R-REM recognition will be examined with a Chi-square analysis comparing counts of BRDS reports from experimental and comparison facilities captured over time, and treated as binary incidents. Reporting implementation will be examined by evaluating the differences between experimental and comparison group staff reports of R-REM, collected over three waves. Individual R-REM reporting will be determined by counting whether any of the staff-reported R-REM indicators are positive. The object of this analysis is not to identify individuals and perpetrators, but to examine the reported events. In modeling R-REM events, a Poisson regression of count data will be performed.

Aim 3: Primary level-4 evaluation of distal outcomes: Summary of the sources of data for determining falls/accidents/injuries and incidents of R-REM: The data used for evaluation of the primary distal outcome and for R-REM reports include (a) self-report among those residents who are capable, (b) Accident and Incident Reports, (c) resident record review, (d) observational data, including the BRDS, and (e) reports from staff. In addition, an environmental evaluation will occur. Data for falls and injuries will be collected via chart review, staff report and residents who can self-report, and from Incident/Accident Reports on an ongoing basis. Resident and staff informant information will be collected at baseline, 6- and 12-month follow-up. Falls will be considered as binomial (any fall) and Poisson distributed (fall counts).

Sample size {14}

Power calculations are provided for the primary distal outcome: falls, including accidents and injuries, also the outcome requiring the largest sample size. Upstate it is expected that an average

of 50 residents per site will be selected for a total of 300. Downstate, the facilities are larger, and it is expected that the average size will be 125 residents or 750 total. The proposed sample size is 6 facilities and 525 residents per arm.

Using the canonical link (Logit), the generalized linear model (GLIMMIX):

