$\eta = \log(p_{ijk} / (1 - p_{ijk})) = \beta_0 + \beta_1 X_{ijk} + FU_{jk}$, where FU_{jk} is a random effect associated with facility and unit.

The formula for the sample size per group using the method of Diggle is:

$m^* = (z_{\alpha} \sqrt{2PQ} + z_{\beta} \sqrt{p_0 q_0 + p_1 q_1})^2 (1 + (n-1)\rho) / (n(p_1 - p_0)^2)$; and using the GEE method:

$m^* = \frac{(Z_{1-\alpha/2} + Z_{1-\beta})^2 (\pi_1 p_0 (1 - p_0) + \pi_0 p_1 (1 - p_1)) (1 + (n-1)\rho)}{2n\pi_0\pi_1(p_0 - p_1)^2}$. The formula below is adjusted with variance inflation factor (V_{if}) and reliability(R_{el}): $m = V_{if}m^* / R_{el}$ and

$$V_{if} = (1 + (n_e - 1)\rho_e)(1 + (n_s - 1)\rho_s n_e p_e / (1 + (n_e - 1)\rho_e))$$

where $n_s = 5$ is the average number of units in the facility, $\rho_s = 0.015$ is the ICC for facility, $n_e = 17$ is the average number of residents in the unit, $\rho_e = 0.03$ is the ICC for unit, and the reliability:

$$R_{el} = 0.95.$$

The following table assumes $\alpha = 0.05$, power $(1 - \beta) = 80\%$, $R = 0.95$ and $V_{if} = 2.5$ (With $n_e = 17$,

$ICC_{Unit} = 0.03$, $N_s = 5$, $ICC_{Facility} = 0.015$, the fall rate at follow-up: $p_0 = 33\%$ and $p_1 = 20.75\%$). Two

scenarios for ρ (the average correlation of the outcomes over waves) were posited:

Group	Fall rate P(y=1)				Diggle Method		GEE Method	
	Baseline Rate	6 Month	12 Month	Combined 6M & 12M	M ($\rho = 0.5$)	M ($\rho = 0.6$)	M ($\rho = 0.5$)	M ($\rho = 0.6$)
Intervention	37%	22%	19.5%	20.75%	404	431	399	425
Usual Care	37%	34%	32%	33%	404	431	399	425

As shown, with 525 per group, power is adequate for intent-to-treat (ITT) analyses, including all respondents. Because randomization is at the facility rather than individual level, there is the potential for imbalance on baseline variables and missing covariate data. Assuming attrition of

15% at wave 1, it is estimated that 445 per group will have at least baseline and one additional wave of data included, using the EM missing data algorithm; thus, power is adequate to detect the posited difference in fall reduction of about 12% even with attrition.

Recruitment

All residents are approached and invited to participate. For those who do not wish to be interviewed, a different or the same interviewer approaches again at another time that may be more amenable to the resident. All resident questions are addressed and interviews occur at a time and place preferred by the resident.

Assignment of interventions: allocation

Sequence generation

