Algorithms for conducting randomization that take into account clustering such as exists with geographical regions and rolling enrollment have been developed by the author. This method has yielded balanced groups for many studies. This randomization procedure will be carried out using a SAS macro after a facility completes the baseline interview. A random number from 0 to 1 will be used to determine the assignment group. The standard cut score will be set at 0.5 for the first n facilities from the same region. Facilities which receive a random number between 0 and 0.5 will be assigned to the usual care group and those with a random number greater than 0.5 will be assigned to the intervention group. The balance between the groups within each group will be carefully weighted after the total number of facilities from a group reaches a number greater than n. Before the randomization procedure, the number of facilities randomized to each arm for each region will be estimated using SAS macro programs. If more than the n facilities are randomized initially, the cut score for the next facility is equal to the ratio of the intervention group (n1) to the facilities already randomized (m) for that group (n1/m). For example, group A region provides eight facilities for randomization and the n is set to 5, the first five facilities (n) will be randomized to the standard cut score 0.5 (about half will go to the intervention and half to the usual care group). The sixth facility's randomization cut score is equal to the number of facilities in the intervention

group (n_1) divided by the total number of facilities randomized within that group (in this case, the denominator m is 5.) The seventh facility's cut score will be adjusted according to the previous six facilities, and so forth.

Concealment mechanism

The biostatistician who runs the randomization procedure passes the information directly to the intervention trainer who alerts the ALRs of their assignment. The principal investigator who oversees the data coordinating centre (DCC) at the Research Division, Hebrew Home at Riverdale (RD-HHAR) is the only other person made aware of the assignment.

Implementation

A biostatistician at the coordinating centre developed and runs the randomization procedure. Randomization occurs at the facility level. Research interviewers who enrol participants are blinded to randomization group.

Assignment of interventions: Blinding

Who will be blinded

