Statistical methods appropriate for clustered data will be used in the primary analysis to compare the groups with respect to the binary outcome. Generalized mixed effects models (MEMs) will be used to test the hypothesis that those assigned to the intervention will experience a significantly higher rate of fall/accident/injury reduction as contrasted with usual care. The outcome will be modeled as a function of intervention, time and their interaction and controlling for the baseline falls. To account for the clustered nature of the outcomes, the models will include random effects for facilities, units and subjects. The models will be fit using mixed effects logistic-regression as implemented in SAS Proc Glimmix. The appropriate covariance structure will be determined. The primary analysis will be supplemented with an exploration of the effect of baseline subject, facility and unit characteristics on the intervention effect. These results will inform generalizability of

intervention effects.

Analyses for secondary outcomes: The proposed secondary outcomes are affect, measured by the FTQ and the NIH PROMIS depression measure,^{61,62,63} and behavior. The reliability estimates of the outcomes are typically at least 0.90. Methods for analyses of treatment effects in pre-post clinical trials, in the context of missing data, have been compared.^{64,65,66,67,68,69} The primary proposed analyses will use MEMs, and a full information likelihood approach, with sensitivity analyses using generalized estimating equations (GEE).

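### The written randomisation rule does not deliver the stated three-per-arm split in each region: at most 55% per region, 30% for both regions, 40% for 6:6 overall

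*Combined protocol and SAP*

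**What the plan says.** Trial design fixes the outcome of the allocation: "Three facilities in each region will be randomized to usual care or to the intervention on a 1:1 ratio". Sample size {14} relies on it, with about 50 residents per facility upstate and 125 downstate: "The proposed sample size is 6 facilities and 525 residents per arm".

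Sequence generation describes how assignments are made. A random number below the cut score sends a facility to usual care, and one above it to the intervention. "The standard cut score will be set at 0.5 for the first n facilities from the same region". After those n facilities, "the cut score for the next facility is equal to the ratio of the intervention group (n1) to the facilities already randomized (m"). On balance, the section adds only that "The balance between the groups within each group will be carefully weighted" and that the numbers going to each arm by region are estimated beforehand with SAS macros. The only value of n is in an example in which "group A region provides eight facilities for randomization and the n is set to 5".

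For the primary falls model, "The outcome will be modeled as a function of intervention, time and their interaction and controlling for the baseline falls", with random effects for facilities, units and subjects.

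**The concern.** The first two sections state an exact split. The third gives a procedure that only leans toward it. Nothing written stops a region from ending 4:2 or 5:1, and because n is unstated the allocation cannot be reproduced from the text.

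With 12 facilities of very unequal expected size by region, a departure changes both the arm sizes and the regional mix of each arm. The power statement assumes equal arms. It is also unclear whether the analysis would absorb a chance difference in regional mix. Trial design calls the regions fixed, but the primary falls model does not list region, and the end of the Statistical models section proposes no covariates beyond baseline values for the main analyses.

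**Working it through.** **Inputs.** Six facilities per region and 3:3 (Trial design). 50 and 125 residents per facility (Sample size). Cut score 0.5 for the first n facilities, then n1/m (Sequence generation). Fall rates 33% and 20.75%, two-sided alpha 0.05, power 80%, variance inflation 2.5, reliability 0.95, correlation between waves ρ = 0.5 or 0.6, and 445 per group after attrition (Sample size). As n is not given, n = 1 to 6 was examined.

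**The plan's own figures reproduce.**
- Arm size: 3 × 50 + 3 × 125 = 525.
- GEE formula with two follow-up waves: 398.0 (ρ = 0.5) and 424.5 (ρ = 0.6), against the stated 399 and 425.
- Diggle formula: 403.4 and 430.3, against 404 and 431.

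**Probability of 3:3 in one region.** With n1 of m facilities already on intervention, P(next to intervention) = 1/2 while m < n, and 1 − n1/m afterwards. For n up to 5, a region reaches 3:3 only if its first five facilities split 3:2 and the sixth goes to the smaller arm, which has probability 3/5. So

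P(3:3) = (3/5) × P(first five split 3:2).

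- n = 5: five fair coins split 3:2 with probability 20/32, so P = 3/5 × 20/32 = 3/8 = 37.5%.
- n = 1 or 2: the recursion gives P(3:2 after five) = 22/24, so P = 3/5 × 22/24 = 11/20 = 55%.
- n = 6 (fair coin throughout): 20/64 = 31.25%.

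Even if the first five always split 3:2, the result could not exceed 60%.

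**Two regions.** Treating them as independent, P(3:3 in both) is the square, 0.55² = 30.25% at best. For 6:6 overall, opposite imbalances may cancel: 0.55² + 2(13/60)² + 2(1/120)² = 39.7% at best.

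| n | 3:3 in a region | 3:3 in both | 6:6 overall | region within one facility of 3:3 | smaller arm expects ≤ 400 |
|---|---|---|---|---|---|
| 1 or 2 | 55.0% | 30.3% | 39.7% | 98.3% | 35% |
| 3 | 52.5% | 27.6% | 37.7% | 97.5% | 37% |
| 4 | 45.0% | 20.3% | 32.9% | 95.0% | 41% |
| 5 | 37.5% | 14.1% | 27.3% | 87.5% | 47% |
| 6 | 31.3% | 9.8% | 22.6% | 78.1% | 53% |

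With facilities at their regional averages, 525 per arm occurs only under 3:3 in both regions. If the cut score is read in the opposite direction, P(3:3) is 0 to 31%.

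**Power.** The plan's GEE variance for unequal arms is

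V = (2.5/0.95) × ((1 + ρ)/2) × (0.2075 × 0.7925/N_I + 0.33 × 0.67/N_U),

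and power = Φ(0.1225/√V − 1.96). Expected arm sizes are multiplied by 445/525. At ρ = 0.5:

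| Allocation | N_I / N_U | Power |
|---|---|---|
| 3:3 in both regions | 445 / 445 | 84.2% |
| 4:2 downstate only, intervention larger | 551 / 339 | 80.7% |
| 4:2 downstate only, usual care larger | 339 / 551 | 83.4% |
| 4:2 in both, intervention larger | 593 / 297 | 77.8% |
| 4:2 in both, usual care larger | 297 / 593 | 81.7% |

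For n = 1 to 5, 4:2 downstate only (either direction) has probability 19% to 24%. Same-direction 4:2 in both regions has 9% to 12.5%. Averaging over all allocations:

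| n | average power, ρ = 0.5 | below 80%, ρ = 0.5 | below 80%, ρ = 0.6 |
|---|---|---|---|
| 1 or 2 | 82.9% | 6.5% | 23.8% |
| 3 | 82.8% | 7.8% | 25.6% |
| 4 | 82.3% | 11.8% | 31.1% |
| 5 | 81.4% | 19.9% | 39.5% |
| 6 | 79.6% | 29.6% | 47.7% |

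At ρ = 0.6 balanced power is 81.8%, and the average is 80.5% to 78.9% for n = 1 to 5.

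**The case against.** The strongest reply is that the consequence is small. The rule pulls toward balance and treats the arms alike. Most misses are one facility, and some cost nothing: 450 intervention against 600 usual care residents before attrition still gives 84.2%. That all stands, and it limits the seriousness of the point.

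The share of allocations below 80% also depends on how close balanced power already is to 80%. At ρ = 0.6 and n = 1 or 2, 23.8% fall below 80%, but only 6.7% below 78% and 1.7% below 75%. The average loss is therefore the better summary.

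The macro may impose a limit that the text does not mention. That is possible, and the finding concerns only the written rule. If such a limit exists, the protocol misdescribes it and a sentence would put that right.

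Region is modelled under Examination of potential region differences, with an interaction tested at α = 0.15. That is a separate examination, with depression and affect as its examples, and it does not place region in the primary falls model.

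Finally, 525 is an expectation from average facility sizes, so forcing 3:3 would not guarantee it, and a soft biased coin is a legitimate method in general. Both are true. But this plan states an exact split, and its rule does not produce one.

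**Conclusion.** The point holds. Under every n from 1 to 6 the planned 3:3 in both regions is a minority outcome: at most 30%, and 14% at the illustrative n = 5. The upper bounds of 55% per region and 40% for 6:6 overall are reached only at n = 1 or 2.

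The cost is moderate: 1 to 3 points of power on average for n = 1 to 5 at ρ = 0.5. At n = 6, where the adaptive step would never operate, the loss is 84.2 − 79.6 = 4.6 points. There is no systematic bias. Any confounding by region depends on a regional difference in fall rate that the documents do not give, and adjustment for baseline falls would partly reduce it.

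The probabilities rest on the written rule with no hidden constraint and independent regions. The power figures also assume average facility sizes, a fixed variance inflation of 2.5, equal proportional attrition and the plan's normal-theory formula. It should be fixed because a stated design property is not delivered and the remedy is cheap.

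**What to change.** Replace the cut-score paragraph with one of the following.

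1. *For each region the biostatistician draws in advance, with equal probability, one of the 20 sequences of six assignments with three intervention and three usual care, holds it, and releases the next assignment after a facility completes baseline.*
2. Keep the biased coin, state n for this trial, and add: *Once an arm has three facilities in a region, the remaining facilities in that region go to the other arm.*

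Either makes P(3:3) = 1 and reconciles Trial design, Sample size and Sequence generation. If the macro already does this, say so. For facilities already randomised, report the realised split by region and include region as a fixed effect in the primary model, amending the primary falls analysis and the no-other-covariates statement to match.

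The cost is one paragraph and a small macro change. The last assignment in a region, and sometimes the last two or three, becomes predictable to those who know the earlier ones: the biostatistician, the trainer and the coordinating centre's principal investigator. The harm is limited because assignment follows baseline and enrolling interviewers are blinded. The region effect uses one between-facility degree of freedom.

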The authors conducted the first systematic, prospective study of resident-to-resident elder mistreatment (R-REM) in nursing homes and have developed novel methodology to identify the phenomenon. Data demonstrated that (1) R-REM is highly prevalent, (2) case finding methodology is greatly enhanced by meaningful participation of front line staff, and (3) paradoxically, higher functioning residents may be at greatest risk for involvement in R-REM (e.g., residents who are ambulatory and capable of wandering as opposed to those who are in the last stages of dementing illness). Additionally, funded by the New York State Department of Health

dementia grants program we developed a three module-program targeting front line staff to implement best practices related to R-REM in long-term services and support (LTSS) settings. Using an experimental design, we tested the intervention in nursing homes. Evaluation of longitudinal outcomes showed significant increases in staff knowledge post training, controlling for pre-training levels for the intervention group and of increased recognition of R-REM, and longitudinal reporting in the intervention as contrasted with the usual care group.¹⁸ Additionally, falls, accidents and injuries were reduced.¹⁹ These findings have important implications for assisted living residences (ALRs) where residents typically have cognitive impairment with better mobility and less staff to intervene in R-REM. The state survey process is also less uniform in ALRs (in comparison to nursing homes) and has not addressed R-REM.

Objectives

The goal of the project is to evaluate a training program for staff that enhances identification and intervention with respect to episodes of resident-to-resident elder mistreatment (R-REM). The hypotheses corresponding to the specific process outcome aims (1 & 2) and primary distal outcome (aim 3) for which the study was powered are:

Aim 1 (A1). Enhance staff knowledge of R-REM

Hypothesis 1: Staff knowledge related to R-REM and R-REM treatment will increase after training.

Aim 2 (A2). Enhance staff recognition, reporting and care planning related to R-REM

Hypothesis 2: Due to the heightened awareness as a result of training, the frequency of reported R-REM in the intervention group will increase, relative to the comparison group after training.

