- 1) If the resident has a perceptual impairment that makes it difficult for her/him to read/sign the Informed Consent Form (e.g., visual impairment)
- 2) If the resident is illiterate, the interviewer reads the Informed Consent Form to the resident

3) If the resident has a physical impairment that prevents her/him from writing (e.g., contractures in both arms, paralysis, etc.)

4) If the resident does not wish to sign the Informed Consent Form, but verbally indicates that s/he is willing to participate in the interview

Per the IRB, in these cases, an observer not associated with the research (e.g., facility staff) must witness the verbal consent process.

Interventions

Explanation for the choice of comparators

After successful implementation of the R-REM research protocol in nursing homes, the authors wanted to further test the intervention in another LTSS setting with a similar population but with less staffing and state oversight. Assisted living was selected because it is an area of LTSS that is growing rapidly both in numbers of facilities and in terms of the populations served.

Intervention description

The intervention, i.e., the training of nursing, social work, administrative and other staff on R-REM is conducted in three separate sessions: 1) Recognition and Risk Factors, 2) Management, and 3) Implementation of Guidelines. The trainer who administers the three modules is an experienced doctoral level, adult education professional who participated in the development and modification of the modules; she has extensive experience in staff training. Modules are provided to facilities randomized to the intervention after the completion of baseline data collection, and to those randomized to usual care after completion of 12-month follow up data collection.

Description of Module 1: Recognizing R-REM: Module 1 covers the extent of R-REM which includes: evidence; risk factors associated with the victims, perpetrators, and environment; and the role of cognitive impairment. Different forms of mistreatment are covered, including physical, psychological, sexual, and theft. This module is delivered in the form of an experiential half-hour in-service training, plus pre- and post-tests designed to be conducted at the ALRs.

Description of Module 2: Management of R-REM

- A. Introduction and review of previous session and pretest
- B. Film on management of elder mistreatment

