A. For each participant, ten five-minute observations are performed by trained interviewers at different times of the day and in different locations in order to obtain additional information about incidents of R-REM and other disturbed behaviours. While episodes of R-REM are likely to be brief and intermittent, based on our experience in the nursing home study, interviewers did observe many incidents of R-REM. The Total Observation Checklist includes 14 affect and 37 behaviour items (Observed Behavior Checklist).⁵³ Frequencies of affective and behavioural states are coded as: “Not at all”, “Very little (1 or 2xs during observation period)”, “With some frequency (several times)”, “With moderate frequency (many times but not continuous)”, or “With great frequency (continuous)”. Typical affect items include: “Crying”; “Agitated”; “Emotionally labile”. Typical behavioural items include: “Disruptive of others”; “Wandering”; and “Argumentative”. In an urban LTSS sample, the Cronbach’s alphas ranged from .74 to 0.85 and from 0.85 to 0.87 in a rural LTSS sample.⁵⁴

B. R-REM behavior recognition and documentation sheet (BRDS): This measure was based on the Shift Coupon, a form originally designed by nursing staff to provide a “quick, easy, anonymous, and non-threatening method to report adverse events,”⁵⁵ and was in the form of a small note pad. BRDSs are intended to measure recognition and capture real time R-REM events. These forms are designed as prescription pads to be carried in the pockets of staff. They are distributed at the training sessions (module 3 for intervention facilities and during the opening of the unit for usual care staff); additional pads are available at a central location. Sheets are torn off after documenting R-REM. Items include: residents involved, identity of the perpetrator, actions involved, location, potential cause, and what did you (staff) do about it. Boxes for completed forms are placed in a designated location on each unit.

C. Event logs: When an event is reported from a) resident interview b) staff interview c) interviewer observation, or d) BRDS, the research interviewer will complete an Event Log worksheet in order to better understand the circumstances of the R-REM event. This form contains descriptive

information about the event, its time and place, the reporting source, the participants, and environmental factors at the time of the event.

4. Chart data

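### BRDS pads are handed out at different, undated events in the two arms, and the Aim 2 comparison of BRDS reports sets no common counting window, denominator or exposure offset

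*Combined protocol and SAP*

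**What the plan says.** All references are to the combined protocol and SAP.

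- **Pad distribution** (Observational Data, item B): intervention staff receive the pads at the module 3 session, and usual-care staff receive them "during the opening of the unit for usual care staff". The phrase about opening the unit occurs only here, with no definition or date.
- **Randomisation** (Sequence generation): "This randomization procedure will be carried out using a SAS macro after a facility completes the baseline interview".
- **Training** (Intervention description): "Modules are provided to facilities randomized to the intervention after the completion of baseline data collection". Module 3 is the last of three separate sessions, and the interval from baseline to module 3 is not given. Usual-care facilities are trained only once their 12-month data are in.
- **Hypothesis 2** (Objectives): "the frequency of reported R-REM in the intervention group will increase, relative to the comparison group after training".
- **Analysis** (Outcomes, Aim 2): a "Chi-square analysis comparing counts of BRDS reports from experimental and comparison facilities captured over time, and treated as binary incidents". The same paragraph adds: "In modeling R-REM events, a Poisson regression of count data will be performed". It does not say whether that model uses BRDS sheets, staff interviews or both. Neither analysis has a stated start date, end date, denominator or offset.

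**The concern.** A count of voluntary reports depends on how long staff have had the means to report. The plan ties that starting point to one event in one arm and to a different event in the other, dates neither, and then compares reports with nothing that adjusts for time at risk. Any gap between the two events would enter the comparison as if it were a difference in recognition.

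There is also a question of feasibility. A facility has no arm until its baseline interviews are done. If opening a unit means starting research work there, nobody can yet identify the usual-care units that should receive pads.

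At stake is the BRDS part of Aim 2, which is the plan's real-time measure of whether training improves recognition.

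**Working it through.** The documents give no expected number of BRDS reports and no power figure for them, so there is no stated figure to reproduce. The check has two parts.

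**1. The timeline, on each reading of unit opening**

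- *Opening before randomisation.* The arm is unknown, so handing pads to usual-care staff alone is impossible. The BRDS item then conflicts with Sequence generation, and it cannot be known what would be done in practice.
- *Opening after randomisation.* The distribution rule can be followed. Usual care then starts at opening and intervention facilities start at module 3. No passage makes these dates coincide, and the analysis has no term for a difference.
- *The wording of Hypothesis 2.* Its restriction to the period after training sets a start in the intervention arm only. Usual care has no training date until after its 12-month data collection, so the phrase cannot supply a common start.

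**2. What a lag would do (illustration)**

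Assumptions, none of them in the documents: usual-care pads are in use from month 0, intervention pads from month *d*, and counting ends at month 12 in both arms. True reporting rates are constant over time and equal between arms, and resident numbers are equal.

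Expected count ratio, intervention to usual care: *r* = (12 − *d*)/12.

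- *d* = 1: 11/12 = 0.92
- *d* = 2: 10/12 = 0.83

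A true reporting ratio of 1.25 would appear as 1.25 × *r*: 1.15 at one month and 1.04 at two.

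Now assume 200 reports in total and test the split between arms against 50:50 at two-sided 0.05, with no offset and no clustering. The expected intervention share is π = *r*/(1 + *r*). The chance of a significant result in the direction of more usual-care reports is

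Φ{[0.5 − 1.96√(0.25/200) − π] / √(π(1 − π)/200)}.

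For *d* = 2, π = 0.8333/1.8333 = 0.4545. The numerator is 0.5 − 0.0693 − 0.4545 = −0.0238 and the denominator is 0.0352, so the chance is Φ(−0.677) = 24.9%.

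| Assumed lag *d* (months) | Count ratio at equal true rates | True ratio 1.25 appears as | Chance of a false result favouring usual care |
|---|---|---|---|
| 0 | 1.00 | 1.25 | 2.5% (nominal) |
| 0.5 | 0.96 | 1.20 | 4.9% |
| 1 | 0.92 | 1.15 | 8.9% |
| 2 | 0.83 | 1.04 | 24.9% |
| 3 | 0.75 | 0.94 | 52.4% |

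With a common counting window or a correct exposure offset, the expected ratio at equal true rates returns to 1.00 whatever *d* is. The last column depends on the assumed 200 reports and ignores clustering, so it is indicative only.

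**The case against.** The strongest reply is that the text does not show unequal windows at all. Unit opening is undefined and could fall after randomisation, at about the time of module 3. The lag could then be nil, and there would be no conflict with Sequence generation. That is correct. A reader might infer that the arm is certainly unknown at opening, or that usual care certainly has a longer window. The documents support neither. The two inferences also sit badly together: if the arm is unknown, pads cannot go to usual care alone, so that reading shows an unworkable instruction and not a longer window.

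Other limits also stand:

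- **Scope.** Aim 2 also uses staff interviews at the three waves. The Staff Informant Interview section gives them a two-week recall period that does not differ by arm, so pad timing does not change what they cover.
- **Metric.** The chi-square treats reports as binary incidents, so a ratio of counts does not carry over directly to that test.
- **Direction.** If usual-care pads come first, the bias works against Hypothesis 2, so the risk is a missed effect. The documents do not fix the sign of the lag any more than its size.
- **Blinding.** A reader might infer that pad timing reveals the arm to interviewers. Interviewers do complete an Event Log for BRDS events, but nothing says that they see when pads arrive, and the blinding section claims blinding only as far as possible. The point is speculative.
- **Falls.** The Aim 3 text lists the BRDS among sources for the primary outcome and R-REM reports jointly, but its sentence on collecting falls and injuries does not name it. An effect on the primary outcome is not established.

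None of this supplies the missing window. On either reading the two arms start on different events, and the analysis has no correction.

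**Conclusion.** The concern holds in a limited form. The plan sets different, undated starting events for BRDS reporting in the two arms and specifies a comparison that cannot correct for a difference between them. If unit opening precedes randomisation, the BRDS item and Sequence generation contradict each other and must be reconciled.

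The size of any bias cannot be stated. It is zero with no lag. The ratios of 0.92 and 0.83 rest on assumed lags of 1 and 2 months, equal and constant true rates, and a common end at month 12. The exposed result is the BRDS comparison, together with the Poisson model to the extent that it uses BRDS sheets. This is a process outcome, and the study is powered on falls. The change is still worth making before the data are analysed, because it is cheap and a lag of a month or two could hide much of a moderate true increase in reporting.

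**What to change.** 1. Define unit opening relative to randomisation, and reconcile the BRDS item with Sequence generation so that the distribution rule can be carried out.
2. Count BRDS sheets in both arms only from a common start to the 12-month visit. In intervention facilities the start is the module 3 date. In usual care it is a date at the matched lag from randomisation. Because sessions are repeated across shifts with makeup sessions, state which session sets the module 3 date for a facility.
3. Replace the chi-square on counts with a Poisson or negative binomial rate model that has a log resident-time offset and accounts for facility clustering. State whose resident time forms the denominator, and say which data source the Poisson model already in the plan uses.

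**Cost.** The change is mainly SAP wording. Sheets completed before the common start drop out of the between-arm comparison, though they can still be described. The date of each event or sheet must be recorded: the plan says that the Event Log holds the time of the event but does not name a date, and its list of BRDS items names none.
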